2.1.2. Endpoints

Primary Endpoint

- The primary endpoint is ORR: the proportion of subjects with a partial response (PR) or complete response (CR) as defined by RECIST 1.1

Secondary Endpoints

- Incidence of adverse events
- DoR: the duration from the date of the initial documentation of a response to the date of the first objectively documented evidence of recurrence or progressive disease or death, whichever status is recorded first.
- CBR: the proportion of subjects who achieve disease control (CR, PR, or SD with duration of at least 16 weeks).
- PFS: the duration from the date of randomization to the date of objectively documented progression or death due to any cause, whichever status is recorded first.
- OS: the duration from the date of randomization to the date of death due to any cause.
- Serum daratumumab concentration (C_{min} , C_{max}) and incidence of anti-daratumumab antibodies
- Serum atezolizumab concentration (C_{min} , C_{max}) and incidence of anti-atezolizumab antibodies

Exploratory Endpoints

- ORR_i: the proportion of subjects with a partial response (PR) or complete response (CR) evaluated by irRECIST
- ORR, DoR, CBR, incidence of adverse events, daratumumab and atezolizumab serum concentration and incidence of anti-daratumumab antibodies and anti-atezolizumab antibodies

Refer to Section 9, Study Evaluations for evaluations related to endpoints.

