9.1.5. Follow-Up Phase

The posttreatment Follow-up Phase will begin once the subject completes the End-of-Treatment evaluation. Reasons for discontinuation of study treatment are listed in Section 10.2. Subjects who discontinue treatment before disease progression must continue to have disease evaluations as described in Table 1 and Section 9.4 (every 6 weeks [± 1 week] for the first 12 months of after the start of treatment and every 9 weeks [± 1 week] thereafter regardless of treatment delays). After disease progression is confirmed, follow-up for survival status and subsequent anti-cancer therapy will be obtained at least every 12 weeks after the last dose of study drug, until the subject has died, is lost to follow-up, or has withdrawn consent. If the information on survival status is obtained via telephone contact, written documentation of the communication must be available for review in the source documents. If the subject has died, the date and cause of death will be collected and documented on the CRF.

The end of the study is anticipated to be 24 months after the last subject has been enrolled (last patient in) or when the last subject has the last assessment in this study (eg, last survival follow-up for the last subject), whichever occurs first.

Investigators may recontact the subject to obtain long-term follow-up information regarding the subject's safety or survival status as noted in the informed consent form (refer to Section 16.2.3, Informed Consent).

Subjects will be instructed that study drug will not be made available to them after they have completed/discontinued study drug and that they should return to their primary physician to determine standard of care.

Beginning with the implementation of Amendment 7, data from safety evaluations performed according to local regulatory approvals and standard of care guidelines^{50,51} will no longer be collected with the exception of serious adverse events that are to be reported and entered in the Sponsor safety repository.

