10.2. Discontinuation of Study Treatment/Withdrawal from the Study

Discontinuation of Study Treatment

A subject will not be automatically withdrawn from the study if he or she has to discontinue treatment. The End-of-Treatment Visit and Follow-up visit assessments should continue as specified in the Time and Events Schedules.

A subject's study treatment must be discontinued if:

- The investigator believes that for safety reasons or tolerability reasons (eg, adverse event) it is in the best interest of the subject to discontinue study treatment
- The subject becomes pregnant
- The subject (or the subject's legally acceptable representative) withdraws consent for administration of study treatment
- The subject experiences unacceptable toxicity, including IRRs described in Section 6.3
- The subject missed more than 2 consecutive planned doses due to daratumumab-related AEs
- The subject missed more than 105 consecutive treatment days due to atezolizumab-related AEs
- The subject experiences confirmed disease progression (per RECIST 1.1), see Table 12.
- A subject who experiences a second primary malignancy that cannot be treated by surgery alone must be withdrawn from the study. However, a subject who develops a malignancy that can be cured surgically may continue to receive the assigned study treatment and should continue to be followed for subsequent progression of NSCLC.

The primary reason for discontinuation of study treatment is to be recorded in the CRF.

Withdrawal From the Study

A subject will be withdrawn from the study for any of the following reasons:

- Lost to follow-up
- Withdrawal of consent to study participation
- Pregnancy
- Second primary malignancy (see Discontinuation of Study Treatment for additional details)
- Death
- The study investigator, for any reason, stops the subject's participation in the study
- Sponsor terminated the study

Before a subject is lost to follow-up, every reasonable effort must be made by the study-site personnel to contact the subject and determine the reason for discontinuation/withdrawal. The measures taken to follow up must be documented.

When a subject withdraws before completing the study, the reason for withdrawal is to be documented in the CRF and in the source document. Study drug assigned to the withdrawn subject may not be assigned to another subject. Subjects who withdraw will not be replaced. If a subject discontinues from treatment, end-of-treatment assessments should be obtained.

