5.3. Major Secondary Efficacy Endpoints

5.3.1. Duration of Response

Definition

Duration of response (DoR) is measured from date of first documented disease response to date of first objectively documented evidence of recurrence or progressive disease or death, whichever occurred first. DoR will be evaluated in subjects who have achieved response of PR or better. Duration of response is calculated in months as follows:

$$\text{DoR} = (\text{date of PD or censoring} - \text{date of first disease response} + 1) / (365.25/12),$$

Deaths due to disease progression will be treated as an event on the date of death, unless disease progression is documented before death. Subjects who start Subsequent anti-cancer treatment for NSCLC will be censored at the last disease assessment no later than the start of Subsequent anti-cancer treatments. Subjects, who are lost to follow-up, withdraw consent, withdraw from study without disease progression, or die due to causes other than disease progression will be censored at the last disease assessment date.

Analysis Methods

The Kaplan-Meier method will be used to summarize DoR for responders in each treatment group. The 25% Quantile, Median, and the 75% Quantile and their corresponding 95% CI will be provided.

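### SAP 5.3.1 censors responders who die of causes other than progression, although its own definition and protocol 2.1.2 end duration of response at death without limiting the cause

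*SAP*

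**What the plan says.** Protocol 2.1.2 runs DoR from the first documented response to the first "objectively documented evidence of recurrence or progressive disease or death, whichever status is recorded first". The first sentence of SAP 5.3.1 gives the same endpoint: "objectively documented evidence of recurrence or progressive disease or death, whichever occurred first". Neither restricts the cause of death.

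The rest of SAP 5.3.1 works differently:

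- Events: "Deaths due to disease progression will be treated as an event on the date of death, unless disease progression is documented before death".
- Censoring of other deaths: responders who "die due to causes other than disease progression will be censored at the last disease assessment date".
- Further grounds for censoring in that sentence: loss to follow-up, withdrawn consent, and a category for those who "withdraw from study without disease progression".
- Formula: the end date is "date of PD or censoring"; death is not named.

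The PFS formula in SAP 5.3.3 does name death beside progression, and the PFS definition there counts death without restriction. Protocol 11.3 says DoR is analysed descriptively among responders and contains no cause-of-death rule.

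**The concern.** A programmer who follows the detailed text of SAP 5.3.1 will not produce the endpoint that the same section defines. A responder who dies without progression, of a cause judged unrelated to the cancer, is a PFS event on the date of death. For DoR the same patient is censored, back-dated to the last disease assessment. Two endpoints that share their terminal events then disagree about one patient.

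Three things are at stake. The reported DoR would not be the protocol endpoint. Event status would depend on the attributed cause of death in an open-label trial, where that attribution can involve judgement. And treating a death during response as if the response might have continued will generally make responses look longer than the definition allows. Comparing DoR between arms is a stated secondary objective, so readers will look at it even though no test is planned.

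**Working it through.** **1. The text.** The conflict needs no arithmetic. Take a responder with no documented progression, no subsequent therapy and no withdrawal, who dies of another cause:

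| Source | Status for DoR |
|---|---|
| Protocol 2.1.2 definition | event at death |
| SAP 5.3.1, first sentence | event at death |
| SAP 5.3.1, event sentence | not covered, because only progression deaths are named |
| SAP 5.3.1, censoring sentence | censored at last disease assessment |
| SAP 5.3.1, formula | no death date to enter |

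Nothing else in either document resolves this.

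**2. Number of responders.** The documents give no planning figure for DoR, so there is none to reproduce. From the sample size assumptions (protocol 11.2: ORR 20% and 40%, 90 subjects, 1:1), expected responders are 45 × 0.20 = 9 in Arm A and 45 × 0.40 = 18 in Arm B. At the third DMC review (44 per arm, protocol 1.4) the same rates give 8.8 and 17.6.

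**3. Size of the tendency, under assumptions.** Assume constant hazards, and let f be the share of response endings that are non-progression deaths. If L is the total hazard, the defined endpoint has median ln2/L. Under the SAP rule the hazard is L(1-f), so the median is longer by the factor 1/(1-f). This ignores the back-dating of the censoring time.

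The documents do not give f; 5% to 20% is an assumed range. The only median DoR in the documents is 17 months, from the phase 1 atezolizumab study PCD4989g (protocol 1.2), and how that study handled deaths is not stated. Taking 17 months as including deaths, L = ln2/17 = 0.0408 per month. Event-free proportions are exp(-Lt) as defined and exp(-L(1-f)t) under the rule:

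| f | Factor on median | 3 months: defined / rule | 10 months: defined / rule |
|---|---|---|---|
| 5% | 1.05 | 88.5% / 89.0% | 66.5% / 67.9% |
| 10% | 1.11 | 88.5% / 89.6% | 66.5% / 69.3% |
| 20% | 1.25 | 88.5% / 90.7% | 66.5% / 72.2% |

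If the 17 months instead excluded such deaths, the defined median would be 17(1-f): 16.2, 15.3 and 13.6 months.

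**4. How many patients.** Per responder, the chance of being reclassified by month t is p = f(1 - exp(-Lt)). With 9 responders and f from 5% to 20%:

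- by 3 months: 0.05 to 0.21 expected; chance of at least one, 1-(1-p)^9, is 5% to 19%;
- by 10 months: 0.15 to 0.60 expected; chance of at least one is 14% to 46%.

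Expected counts double with 18 responders. With all 9 at risk, one such death is a step of 1/9, or 11 points, in the Kaplan-Meier curve as defined, and no step under the rule.

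**5. A sample quantile can move the other way.** Back-dated censoring removes the patient from the risk set before the death. A constructed example with 9 responders: progression at months 2, 3, 5, 9 and 13; censored at 4, 12 and 14; one non-progression death at 10, last assessed at 8.5. Up to month 5 both versions give 8/9 × 7/8 × 5/6 = 0.648.

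- As defined: month 9, five at risk, 0.648 × 4/5 = 0.519; month 10, four at risk, 0.519 × 3/4 = 0.389. Median 10 months.
- Under the rule: month 9, four at risk, 0.648 × 3/4 = 0.486. Median 9 months.

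So lengthening is the general tendency, not a certainty in every sample.

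**The case against.** The fairest reply is that this is a small matter. DoR is descriptive, untested and confined to responders. OS and the deaths table (SAP 6.2) would show every death, and in the main illustration with 9 responders the most likely number of reclassified deaths is none. That stands, and it limits the severity. It does not answer the contradiction.

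It can also be said that the words *any cause* appear in protocol 2.1.2 for PFS and OS but not for DoR. That is true: any death is the natural reading of an unqualified term, not the literal text. If a narrower endpoint was intended, both definitions would have to say so, and the passages would still need reconciling. The formula might be excused as shorthand, since a following sentence makes progression deaths events; it is then an omission to tidy in the same edit rather than a separate fault.

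A reader might infer that deleting the death clause would not be enough, because protocol 10.2 introduces a list with "A subject will be withdrawn from the study for any of the following reasons" and that list includes death, while SAP 5.3.1 censors study withdrawals. The documents do not bear that out firmly. SAP 5.3.1 names withdrawal and death as separate items, and protocol 10.1 includes subjects who died before the end of the study in its description of completion. It is a possible ambiguity, worth a clarifying phrase.

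**Conclusion.** Wrong as written, and should be fixed. SAP 5.3.1 contradicts its own definition and protocol 2.1.2, and that conclusion rests on the text alone. The size is unknown. Inflation of the median by 5% to 25% holds only for f between 5% and 20% with constant hazards; f has no source in the documents, and the 17-month median comes from another study.

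Two stronger readings are tempting and should not be made. One is that reported DoR is longer in any arm that has such deaths: in samples of about 9 to 18 responders a quantile can be longer, unchanged or occasionally shorter. The other is that the rule flatters the combination arm because the DMC noted numerically more deaths there (protocol 1.4). The documents do not say whether any of those deaths were in responders without progression, nor give their causes, so no direction between arms follows.

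The primary ORR analysis, the sample size, OS (SAP 5.3.4) and the general PFS rule (SAP 5.3.3) are unaffected.

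**What to change.** In SAP 5.3.1:

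1. Replace the sentence on progression deaths with one saying that death without prior documented progression is an event on the date of death, whatever the cause, unless one of the section's existing censoring events came first (start of subsequent anti-cancer treatment, withdrawal of consent, withdrawal from the study, loss to follow-up).
2. Delete from the censoring sentence the clause on deaths from causes other than progression.
3. Write the end date in the formula as PD/death or censoring, matching SAP 5.3.3.

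As optional tightening, state that withdrawal from the study here excludes withdrawal because of death. The present rule may be kept as a labelled sensitivity analysis.

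The cost is three wording edits and a small change to the DoR derivation. Protocol 9.1.5 already provides what is needed: "If the subject has died, the date and cause of death will be collected and documented on the CRF".

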5.3.2. Clinical Benefit Rate

Definition

Clinical benefit rate is defined as proportion of subjects who achieve disease control (CR, PR, or SD).

Analysis Methods

Analysis will be based on the ITT population, and response evaluable population. The number and percentages of subjects achieving clinical benefit will be provided by treatment group. In addition, two-sided 95% exact CI will also be provided. Odds ratio of achieving response for Arm B over Arm A, and its 95% confidence interval will be calculated, similar to ORR.

Stratified analysis may also be performed as sensitivity analysis.

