The primary analysis population for the efficacy endpoint will be the intent-to-treat population in the randomized phase of the study. Assuming that the ORR for atezolizumab monotherapy is approximately 20%, and the addition of daratumumab would improve ORR by 20% to 40%, 90 subjects need to be randomized with a 1:1 ratio in order to achieve 80% power to detect this difference with a one-sided alpha of 0.10.

Number and percent of subjects in each response category will be tabulated, along with those for subjects who achieve overall response (CR or PR) and who achieve disease control (ie, CBR: CR, PR, or SD that lasts at least 16 weeks). Odds ratio and its 95% confidence interval will be provided as a measure of treatment effect. Descriptive summaries (mean, standard deviation, median, and range) will be provided for time to response among those subjects who have CR or PR. The primary hypothesis is that daratumumab in combination with atezolizumab will significantly improve ORR compared to atezolizumab alone in subjects with NSCLC.

Table 1: Time and Events Schedule – Safety Run-in, Randomized Arms

Beginning with the implementation of Amendment 7, subjects who continue to derive benefit from atezolizumab treatment, may continue to receive atezolizumab under the supervision of treating investigators in accordance with local regulatory approvals and standard of care guidelines.^{50,51} Data from efficacy and safety evaluations performed according to local regulatory approvals and standard of care guidelines^{50,51} will no longer be collected with the exception of serious adverse events that are to be reported and entered in the Sponsor safety repository.

Assessments	Prescreening (optional)	Screening		Treatment Period (21-day cycles)						EOT (30 +7d after last dose)	Follow-up Period	
				Arm	Cycles 1-3				Cycle 4 and beyond		Pre-PD	Post-PD Survival
					D1 (±3)	D2	D8 (±1)	D15 (±1)				
Day	Any time prior to start of Screening	-56 to -1	-28 to -1									
Procedures												
For every cycle, study procedures may occur ±3 days of the scheduled Day 1 dose, but prior to study drug administration (except for those routinely needed after administration), in order to accommodate the schedule of the site or subject. For Cycles 1 to 3, Day 8 and Day 15, study procedures may be done ±1 day of the scheduled dose, but prior to daratumumab administration. Day 2 visit is only required for Safety Run-in and Arm B subjects during Cycle 1 only.												

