Tumor assessment CT or MRI imaging of all disease sites documented at Screening should be performed using the same methodology throughout the study. Tumor assessments will be performed per RECIST 1.1. For subjects who discontinue treatment for reasons other than progression (eg, adverse event), tumor assessments will continue to be performed until documented disease progression or a new cancer therapy is initiated.			CT or MRI of head, chest, abdomen, and pelvis are required. Include neck if clinically indicated and any other known site of active disease.		X CT or MRI of chest and abdomen (and known sites of active disease) Every 6 weeks (±1 week) for the first 12 months of treatment and every 9 weeks (±1 week) thereafter regardless of treatment delays. Same frequency for all subjects. Imaging timepoints should be calculated from the date of C1D1.							

Table 1: Time and Events Schedule – Safety Run-in, Randomized Arms

Beginning with the implementation of Amendment 7, subjects who continue to derive benefit from atezolizumab treatment, may continue to receive atezolizumab under the supervision of treating investigators in accordance with local regulatory approvals and standard of care guidelines.^{50,51} Data from efficacy and safety evaluations performed according to local regulatory approvals and standard of care guidelines^{50,51} will no longer be collected with the exception of serious adverse events that are to be reported and entered in the Sponsor safety repository.

Assessments	Prescreening (optional)	Screening		Treatment Period (21-day cycles)						EOT (30 +7d after last dose)	Follow-up Period	
				Arm	Cycles 1-3				Cycle 4 and beyond		Pre-PD	Post-PD Survival
					D1 (±3)	D2	D8 (±1)	D15 (±1)				
Day	Any time prior to start of Screening	-56 to -1	-28 to -1									
Laboratory Assessments:												

 - Refer to Inclusion Criterion 6 for specific laboratory values that must be met prior to first dose of study drug administration. - C1D1 laboratory assessments (hematology, chemistry) may be omitted if Screening tests were performed ≤ 7 days prior to the first administration of study drug and the results meet eligibility criteria. After Cycle 1, predose laboratory tests can be conducted up to 72 hours prior to dosing. Laboratory test results must be reviewed by the investigator or qualified designee and found to be acceptable prior to administration of each dose of study drug. 												

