Preliminary results suggest that PD-L1 expression in tumor tissue is likely to be associated with response to atezolizumab. Table 3 summarizes the overall response rate (ORR) by PD-L1 tumor expression in NSCLC patients in the Phase 1 study (PCD4989g), in which atezolizumab monotherapy is administered to patients with locally advanced or metastatic solid tumors or hematologic malignancies. As of the clinical cutoff date, 8 of 20 patients have continued to respond after 7+ to 27+ weeks. The median duration of response (DoR) is 17 months. The most frequently reported adverse events (occurring in $\geq 10\%$ of patients) included fatigue, decreased appetite, nausea, pyrexia, constipation, and cough.

Table 3: Patients with NSCLC in Study PCD4989g: Confirmed Objective Response Rate by Tumor PD-L1 Expression and Best Overall Response Rate (per RECIST, Version 1.1)

PD-L1 IHC Expression Category	ORR (n = 88)	PR	SD
TC3 or IC3	50% (11 of 22) 95% CI: 28.2%–71.8%	50% (11 of 22)	18.2% (4 of 22)
TC3 or IC2/3	31.6% (12 of 38) 95% CI: 17.5%–48.6%	31.6% (12 of 38)	28.9% (11 of 38)
TC0/1/2 and IC0/1/2	12.1% (7 of 58) 95% CI: 5.7%–22.5%	12.1% (7 of 58)	36.2% (21 of 58)
TC0/1/2 and IC0/1	14.3% (6 of 42) 95% CI: 6.4%–27.7%	14.3% (6 of 42)	33.3% (14 of 42)

IC=tumor-infiltrating immune cell; IHC=immunohistochemistry; NSCLC=non-small cell lung cancer; ORR = objective response rate; PD-L1=programmed death-ligand 1; PR=partial response; RECIST=Response Evaluation Criteria in Solid Tumors; SD=stable disease; TC=tumor cell.
Notes: This table is based on a data cutoff date of 21 April 2014 of patients with NSCLC dosed by 21 October 2013. Objective response is per RECIST 1.1.

Single-Agent Clinical Activity in Patients with Advanced or Metastatic NSCLC in Study GO28753 (POPLAR)

GO28753 (POPLAR) is a randomized Phase 2 study in advanced or metastatic NSCLC patients who failed prior platinum therapy (Ferenbacher 2016).¹⁵ Two hundred eighty-seven (287) patients were enrolled and randomly allocated to atezolizumab or docetaxel in a 1:1 ratio. At a minimum follow-up of 13 months (60% of patients had died), atezolizumab significantly improved overall survival compared with docetaxel (12.6 vs 9.7 months; HR 0.73 [95% CI 0.53, 0.99], $p=0.04$). The overall survival benefit from atezolizumab increased with increasing PD-L1 expression on tumor cells, tumor infiltrating immune cells, or both.

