3.2. Study Conduct After DMC Recommendations

As of 25 May 2018, the Sponsor terminated further enrollment into this study. Ongoing treatment with daratumumab will be discontinued in all active subjects receiving combination therapy (subjects randomized to the combination Arm B, as well as subjects randomized to Arm A who have crossed over into Arm B). Crossover to Arm B is also no longer permitted. Ongoing subjects will be given the option to continue on atezolizumab monotherapy until the subject meets one or more of the treatment discontinuation criteria in Section 10.2. For subjects remaining on the study, protocol procedures and the atezolizumab dosing schedule will continue according to Section 9.2 and the Time and Events Schedule (Table 1) until locking of the clinical database. All procedures outlined in previous versions of this protocol pertaining to patients randomized to treatment other than atezolizumab monotherapy (in Table 2 through Table 7, which were removed beginning with the implementation of Amendment 6) will no longer be performed. For safety reporting changes, see Section 12.4. Upon clinical database closure, only serious adverse events will be reported and entered in the Sponsor safety repository for subjects who continue to be treated according to local regulatory approval and standard of care guidelines.^{50,51}

The changes to study conduct and status implemented in Amendment 7 were also pursuant to these recommendation from the DMC.

A clinical study report (CSR) will be prepared based on the interim analysis data reviewed by the DMC at the third DMC review (prior to discontinuation of enrollment and daratumumab dosing).

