5. TREATMENT ALLOCATION AND BLINDING

Procedures for Randomization and Stratification

Following the safety run-in, central randomization will be implemented in this study. Subjects were stratified by PD-L1 status (TC0 and IC0 vs other), histology (squamous vs. non-squamous), and number of prior therapies received (1 vs. >1) and assigned randomly 1:1 using permuted blocks to 1 of 2 treatment groups based on a computer-generated randomization schedule prepared before the study by or under the supervision of the Sponsor. Pursuant to DMC recommendations after the first interim analysis of study data, enrollment was closed to subjects with PD-L1 score of TC0 (Section 4) as of 16 Jan 2018. Therefore, subjects will be stratified by histology (squamous vs. non-squamous), and number of prior therapies received (1 vs. >1).

The interactive web response system (IWRS) will assign a unique treatment code, which will dictate the treatment assignment and matching study drug kit for the subject. The requestor must use his or her own user identification and personal identification number when contacting the IWRS and will then give the relevant subject details to uniquely identify the subject.

As of 25 May 2018, this study was closed to further enrollment.

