11.3. Efficacy Analyses

The primary endpoint will be evaluated after approximately 90 subjects have been enrolled. The DMC will perform additional interim analyses after approximately 40 subjects and 60 subjects have had at least 1 disease assessment, respectively. These analyses will include an evaluation of efficacy as a function of PD-L1 expression. Based on these results, the DMC may recommend restricting enrollment of subjects in PD-L1 subgroups in whom clinical benefit is not demonstrated or expanding enrollment by a maximum of 100 subjects in PD-L1 subgroups without adequate enrollment (see Section 11.2) in accordance with the product label of the Ventana SP-142 assay. Study sites will be notified in writing of any changes to enrollment based on DMC recommendations.

Number and percent of subjects in each response category will be tabulated, along with those for subjects who achieve overall response (CR or PR) and who achieve disease control (ie, CBR: CR, PR, or SD with duration of at least 16 weeks). Odds ratio and its 95% confidence interval will be provided as a measure of treatment effect. Descriptive summaries (mean, standard deviation, median, and range) will be provided for time to response among those subjects who have CR or PR.

For time-to-event endpoints (PFS, OS, and duration of response), Kaplan-Meier estimates of the survival functions will be presented. For PFS and OS, Cox's regression will be performed to obtain the hazard ratio estimate and the corresponding 95% CI, which will be used as a measure for treatment effect. Additional Cox's regression may be performed to include appropriate baseline prognostic variables. Furthermore, exploratory analyses for OS may be performed to adjust for the effect of crossover. Analysis of duration of response will be performed descriptively among those subjects who achieve CR or PR.

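### SAP 5.3.2 counts any stable disease as clinical benefit, whereas the protocol requires at least 16 weeks of it, so the CBR programmed from the SAP would be a different secondary endpoint

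*SAP*

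**What the plan says.** SAP Section 5.3.2: "Clinical benefit rate is defined as proportion of subjects who achieve disease control (CR, PR, or SD". The bracket closes directly after SD. The same section plans a rate with an exact 95% confidence interval for each arm and an Arm B over Arm A odds ratio. The response table in SAP Section 5.2 also has a CBR row, again with no duration.

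The protocol says otherwise in every place where it defines the endpoint:

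- Section 2.1.2, Secondary Endpoints: "CBR: the proportion of subjects who achieve disease control (CR, PR, or SD with duration of at least 16 weeks". The synopsis endpoint list has the same wording.
- Synopsis, Statistical Methods: "CBR: CR, PR, or SD that lasts at least 16 weeks".
- Section 11.3, Efficacy Analyses: "CBR: CR, PR, or SD with duration of at least 16 weeks".

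Comparing CBR between the arms is a secondary objective in both documents, and the SAP places it under its major secondary efficacy endpoints. The tumor assessment row of protocol Table 1 sets the scan schedule: "Every 6 weeks (±1 week) for the first 12 months of treatment and every 9 weeks (±1 week) thereafter", counted from Cycle 1 Day 1.

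**The concern.** The SAP is the document that gets programmed. As written, it removes the durability condition from a named secondary endpoint and keeps the endpoint's name. A reader of the results would take CBR to mean the protocol's variable, but the rate, its interval and the odds ratio would describe another one.

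The condition matters here because the trial is open-label and response is read by the investigator. One early stable reading is weaker evidence of benefit than four months of control. An any-SD CBR is also just the sum of the CR, PR and SD rows that SAP 5.2 already tabulates, so it adds nothing to that table.

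**Working it through.** **1. The plan's own figures.** The documents state no rate, power or sample size for CBR. The only sample size is for ORR (20% against 40%, one-sided alpha 0.10, 80% power, 90 subjects). It reproduces: (1.2816 + 0.8416)² × (0.2×0.8 + 0.4×0.6) / 0.2² = 45.08 per arm, about 90 in total. Power at 45 per arm with pooled variance is 79.0%. This figure stands and does not depend on how CBR is defined.

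**2. Does SD already imply 16 weeks?** No. Protocol Attachment 5 defines SD by change in lesion size only. The first three scans fall at weeks 6, 12 and 18, each ±1 week, so in windows 5–7, 11–13 and 17–19. A subject stable at the first scan meets the SAP rule at week 5 to 7. If SD is measured to the last stable scan, the second scan gives at most 13 weeks, which is less than 16. The protocol condition is then first met at the third scan, week 17 at the earliest.

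**3. Direction.** Every protocol success is also an SAP success. Therefore SAP rate − protocol rate = share of subjects with best response SD lasting under 16 weeks, which is ≥ 0 in each arm. The effect on the odds ratio depends on how these subjects split between arms, which is unknown.

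**4. Size, illustration A (protocol Table 3, earlier phase 1 study).** The table's complementary PD-L1 groups sum to 22 + 58 = 38 + 42 = 80, although its header says 88.

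- Response: (11 + 7)/80 = (12 + 6)/80 = 18/80 = 22.5%
- Any SD: (4 + 21)/80 = (11 + 14)/80 = 25/80 = 31.25%
- SAP-style CBR: 22.5 + 31.25 = 53.75%
- Protocol CBR: 22.5 + s × 31.25, where s is the share of SD lasting 16 weeks. The documents do not give s.

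| s (assumed) | Protocol CBR | SAP excess, points | Subjects per 44 |
|---|---|---|---|
| 0.25 | 30.3% | 23.4 | 10.3 |
| 0.50 | 38.1% | 15.6 | 6.9 |
| 0.75 | 45.9% | 7.8 | 3.4 |

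The limits s = 0 and s = 1 give 22.5% and 53.75%, so without an assumption on s the excess lies between 0 and 31.25 points. The 44 per arm is the number at the third DMC review (protocol Section 1.4).

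**5. Size, illustration B (protocol Table 4).** Six-month PFS in the second-line and third-line-plus columns is 29% to 39%. Assume exponential PFS, S(t) = p^(t/6 months).

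- Week 6: 75.2% to 80.5%
- Week 16: 46.8% to 56.1%
- Drop between them: 28.4 to 24.4 points, or 12.5 to 10.7 of 44

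This is an approximate upper bound on early-progressing subjects reclassified, because responders who progress before week 16 count under both definitions.

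**6. Follow-up at the reporting cut.** Protocol Section 3.2: "A clinical study report (CSR) will be prepared based on the interim analysis data reviewed by the DMC at the third DMC review". That review was on 23 May 2018.

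- 23 May − 112 days = 31 January 2018. Anyone first dosed later could not have 16 weeks of follow-up.
- 23 May − 119 days = 24 January 2018. Anyone first dosed later could not have an in-window week-18 scan.

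These are the latest possible dates, since the data cut precedes the review. Protocol Section 5 says "enrollment was closed to subjects with PD-L1 score of TC0 (Section 4) as of 16 Jan 2018", so subjects dosed after these dates should be TC1-3. An earlier cut could also bring in late TC0 subjects. Neither the cut date nor the number affected is given. SAP 5.1.2 plans no imputation of missing efficacy values and has no rule for such subjects.

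**The case against.** The mismatch itself is hard to dispute. It is not a redaction or a broken table. An outdated protocol base is an unlikely explanation, because SAP Section 1.4 carries the current sample-size text, including the TC2/TC3 expansion. The serious objections concern weight.

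- **Limited consequence.** CBR has no alpha, power or planned test. SAP 5.2 shows CR, PR and SD separately, so a reader can see how much of CBR is SD. SAP 5.3.3 gives Kaplan-Meier PFS at 3 and 6 months, which carries some information on durable control. All of this stands, but none of it supplies the 16-week rate or its odds ratio.
- **Unknown size.** The share of SD lasting 16 weeks is not in the documents, the 25% to 75% range is chosen, and Table 3 counts confirmed responses in a different study ("Confirmed Objective Response Rate by Tumor PD-L1 Expression and Best Overall Response Rate"). This stands, so the figures are illustrations. They also concern the level within an arm, while the objective is the difference between arms.
- **Plan, not result.** The documents show what would be computed, not what was reported. This stands.
- **Unseen specifications.** The data presentation specifications might settle some derivations. SAP 2.5 cites them for imputation only, and they would not be expected to overrule an endpoint definition in the SAP.
- **Derivation rules.** The protocol does not say how SD duration is measured either, so those details are additions and not contradictions. This also stands.

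**Conclusion.** The concern holds. SAP 5.3.2 defines a different endpoint from the one the protocol specifies four times, and the SAP neither acknowledges nor explains the change. Followed as written, it gives a CBR equal to or higher than the protocol's in each arm, with a different interval and possibly a different odds ratio.

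From the Table 3 illustration the excess is between 0 and about 31 points. It is 7.8 to 23.4 points, about 3 to 10 subjects per arm of 44, if 25% to 75% of SD lasts 16 weeks. Those figures rest on that assumed share and on borrowing response and SD rates from another study. The direction of the definition effect on the rate rests on no assumption. The trial's primary conclusion is not at risk, but the definition should be corrected.

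**What to change.** In SAP 5.3.2, restore the protocol's requirement that SD last 16 weeks or longer, and use that variable for the CBR row in 5.2 and for the CBR odds ratio. If the any-SD rate is wanted, report it separately as disease control rate.

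To make the restored definition programmable, it would help to state:

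1. whether the 16 weeks start at randomization or Cycle 1 Day 1;
2. whether SD ends at the last stable scan or at progression. A subject stable at week 12 who progresses at week 18 fails under the first rule and passes under the second;
3. how the ±1-week scan window is treated;
4. how missing scans are handled;
5. how ongoing SD with under 16 weeks of follow-up at the cut is counted, for example as non-success in the ITT set with the number shown by arm.

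The cost is one derived variable, a few lines of rules, and a CBR that is lower or unchanged. No sample size, power or other endpoint changes.
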